## **17 Ethics**

The study will be conducted in accordance with the Declaration of Helsinki Ethical Principles for Medical Research involving Human Subjects (64th WMA General Assembly, Fortaleza, Brazil, October 2013).

### **17.1 Independent Research Ethics Committees (REC)**

Prior to commencement of the study, the protocol, any amendments, subject information and informed consent and assent forms, any other written information to be provided to the subject, subject recruitment procedures, current investigator CVs, and any other documents as required by the relevant Research Ethics Committee will be submitted. Written approval will be obtained from the relevant Ethics Committee prior to the commencement of the study. Any additional requirements imposed by the REC or regulatory authority shall be followed.

## **17.2 Informed consent of study subjects**

In obtaining and documenting informed consent, the investigator will comply with the applicable regulatory requirements and will adhere to ICH GCP standards and to the ethical principles that have their origin in the Declaration of Helsinki. Prior to the start of the study, the Investigator will obtain favourable ethical opinion of the written informed consent form, assent form and any other written information to be provided to subjects.

Subjects and parents/guardians will be given full verbal and written information regarding the objectives and procedures of the study and the possible risks involved. The study team will avoid any coercion or undue improper inducement of the subject to participate and subjects and parents/guardians will be given ample time to consider participation in the study.

If the family decides to participate in the study, the parents or legal representatives will be asked to sign the informed consent form before study-specific procedures are initiated. Whenever possible and according to local laws and recommendations of the local Ethics Committees, the assent of the subjects will be obtained in addition to the consent of the parents or legal representatives. All subjects will receive a copy of the informed consent/assent form, and the Project Coordinator's office will hold copies of the consent/assent forms and Ethics Committee approvals and make them available upon request.

For participants wishing to continue with the extension phase of the study, further written consent/assent will be obtained from parents/guardians and participants. The signed informed consent forms will be photocopied, originals filed in the Investigator's Site File, a copy placed in the patient's notes and a copy given to the subjects.

All subjects will have the right to leave the study at any time, without stating any reason, and without any negative consequences to their subsequent medical

treatment. The subject and/or their legal representative will be informed in a timely manner should any new information become available during the course of the study that may affect their well-being, safety and willingness to participate in the study.

## **18 Amendments to the Protocol**

Any substantial amendments to the protocol and other documents shall be notified to, and approved by, the Research Ethics Committee, and the regulatory authority, prior to implementation as per nationally agreed guidelines.

## **19 Deviations from Protocol**

Deviations from the protocol should not occur without prior approval of the REC or sponsor except under emergency circumstances, to protect the rights, safety and well-being of subjects. If deviations do occur, they will be documented, stating the reason and the date, the action taken, and the impact for the subject and for the study. The documentation will be kept in the Investigator's Site File. Deviations will be logged electronically and will require chief investigator or local principal investigator acknowledgement and sign-off.

Deviations affecting the subject's rights, safety and well-being or the scientific integrity of the study will be reported to the REC and sponsor as soon as possible in a timely manner, following nationally-agreed guidelines.

## **20 Study Management**

### **20.1 Data and Safety Monitoring Board (DSMB)**

An independent Data Safety Monitoring Board (DSMB) will comprise an independent chairperson and two external experts. The DSMB aims to safeguard the interests of trial participants, assess the safety and efficacy of the interventions during the trial, and monitor the overall conduct of the clinical trial.

The DSMB should receive and review the progress and accruing data of the project clinical trials and provide advice on the conduct of the trial. The DSMB will be informed of all serious adverse events and any unanticipated adverse device effects that occur during the study and will review compiled adverse event data at periodic intervals.

## **20.2 Trial Steering Committee (TSC)**

The Trial Steering Committee (TSC) will provide the overall supervision of the clinical trial. The TSC will comprise an independent chairperson, the Chief Investigator, and the leaders of work packages (WP) 2 (pilot study), WP3 (main study) and WP4 (data management) of the KidsAP consortium. The TSC will monitor clinical trial progress and conduct and advise on scientific credibility. The TSC will consider and act, as appropriate, upon the recommendations of the Data Safety and Monitoring Board (DSMB) and ultimately carries the responsibility for deciding whether a trial needs to be stopped on grounds of safety or efficacy.

The TSC will meet (in person or conference call) at regular intervals during the preparation of the study and follow up to discuss the operational aspects of the study. The Principal Clinical Investigators may also participate. The TSC will report its decisions to the Ethical Board and the General Assembly of the KidsAP Consortium.

## **20.3 Study Monitoring**

The Study Coordinator will ensure that the study is conducted in accordance with ICH GCP standards through site monitoring visits. A monitoring plan will be written and agreed prior to randomisation.

# **21 Responsibilities**

## **21.1 Chief Investigator**

The Chief Investigator (CI) is the person with overall responsibility for the research and all ethical applications will be submitted by the CI. The CI is accountable for the conduct of the study and will ensure that all study personnel are adequately qualified and informed about the protocol, any amendments to the protocol, the study treatments and procedures and their study related duties. The CI should maintain a list of appropriately qualified persons to whom he/she has delegated specified significant study-related duties.

## **21.2 Principal Clinical Investigator**

The Principal Clinical Investigator will be responsible for the day-to-day conduct of the clinical aspects of the study.

### **21.3 Study Coordinator**

The Study Coordinator will provide day-to-day support for the study and provide training through Principal Investigator meetings, site initiation and routine monitoring visits.

## **22 Reports and Publications**

Data will be submitted for publication in internationally peer-reviewed scientific journals; members of the investigator group will all be co-authors. The privacy of each subject and confidentiality of their information shall be preserved in reports and publication of data.

## **23 Timetable**

Inclusion of the first subject in the study is planned to take place in January 2019. The expected completion of the last subject is April 2021 and the planned completion of the Clinical Study Report is October 2021.

The expected completion of the last participant in the extension phase is October 2022.

## **24 Retention of Study Documentation**

Subject notes must be kept for the maximum time period as permitted by each relevant institution. Other source documents and the Investigator's Site File must be retained for at least 15 years, in line with the General Data Protection Regulation (GDPR) (EU) 2016/679. The Principal Investigator will archive the documentation pertaining to the study after completion or discontinuation of the study.

## **25 Indemnity Statements**

Indemnity for any harm arising from the conduct of research will be provided according to local arrangements in respective centres.

- Cambridge, UK - National Health Service indemnity cover will apply for any claims arising from management and conduct of research. Any liability arising from study design will be covered by the clinical trial insurance policy organised by the University of Cambridge.

- Graz, Innsbruck, Vienna, Austria – Subjects will be insured according to Medical Device Law § 47 (StF: BGBI. Nr. 657/1996, BGBI. I Nr. 143/2009)
- Leipzig, Germany - Subjects will be insured according to the German Medical Device Law (MPG). Any liability arising from the study will be covered by the clinical trial insurance policy organized by the University of Leipzig.
- Luxembourg - Centre Hospitalier de Luxembourg indemnity will apply for any claims arising from the management and conduct of research. Any liability arising from the study design will be covered by the clinical trial insurance policy organised by the Centre Hospitalier de Luxembourg (Amlin Corporate Insurance NV).

## Revision History

The following table outlines changes made to the Statistical Analysis Plan.

Version Number	Author	Approver	Effective Date	Study Stage
1.0	[name]	[name]	04/04/2019	Protocol development
1.1	[name]	[name]	06/19/2019	Enrollment
1.2	[name]	[name]	07/11/2019	Enrollment
1.3	[name]	[name]	07/13/2020	Follow-up
2.0	[name]	[name]	09/01/2020	Follow-up
3.0	[name]	[name]	05/05/2021	Initial SAP analyses completed

Version Number	Revision Description
1.1	Clarified when the end of the period occurs for safety analyses and that secondary analyses by time of day include the same subjects as the primary analysis
1.2	Clarified the scoring of the INSPIRE survey
1.3	Added in the questionnaires for the sleep sub-study. Changed the definition of daytime and nighttime to be consistent with the protocol.
2.0	Added in analyses for the extension phase
3.0	Added post-hoc secondary insulin analyses in Units/kg/day. Added post-hoc secondary insulin analyses in Units/kg/day by time of day. Added in post-hoc tabulation of basal and bolus in Units/kg/day by time of day. Clarified analyses of secondary HbA1c and clinical outcomes.

23

24

[name]  
I am electronically signing this document  
2021-05-05 16:48:04:00

25 Author: \_\_\_\_\_

26

27

[name]  
I am digitally signing this document

28  
29 Senior Statistician: \_\_\_\_\_ 2021-05-05 18:51:04:00

30

31 Jaeb Principal Investigator: \_\_\_\_\_

32

33 **1. Overview**

34 This document outlines the statistical analyses to be performed for the KidsAP02 study. The  
35 approach to sample size and statistical analyses for this study are summarized below.

36 This is an open-label, multicenter, randomized, two period crossover study to assess the efficacy  
37 and safety of closed loop (CL) insulin delivery in comparison with sensor augmented/insulin  
38 pump (SAP) therapy with continuous glucose monitoring (CGM) over four months in children  
39 with type I diabetes aged 1-7 years. Approximately 72 subjects are expected to be randomized  
40 and enter the trial. All participants will receive both interventions, and the order of receiving  
41 them will be randomized based on a 1:1 ratio. Randomization will be preceded by a 2-4 week  
42 run-in period where subjects must demonstrate competency and compliance in using the study  
43 insulin pump and CGM device. After randomization, the subjects will enter the two four month  
44 study periods and will test one intervention per study period. The two periods will be separated  
45 by a 1-4 week washout period. The study also includes an optional extension phase where the  
46 participants continue CL system usage for an additional 18 months after completing the  
47 randomized trial. The purpose of the extension phase will be to compare the efficacy and safety  
48 of continued CL system use to SAP therapy as assessed during the main study.

49 **2. Statistical Hypotheses**

- 50 • *Null Hypothesis*: There is no difference in the true mean time spent in the target range  
51 (3.9 to 10.0 mmol/L) over the four month period between the two treatment groups.
- 52 • *Alternative Hypothesis*: There is a nonzero difference in the true mean time spent in the  
53 target range over the four month period between the two treatment groups.

54 **3. Sample Size**

55 The study is projected to randomize 72 subjects. The sample size was calculated assuming 90%  
56 power, a treatment effect of 5% in the percentage of time in the target range, a standard deviation  
57 of 10.3% for an individual measurement, and a correlation of 0.3 between periods.

58 **4. Outcome Measures**

59 **Primary Efficacy Endpoint:**

60 Time spent in the target range (3.9 to 10.0 mmol/L) over the four month period

61 **Other Key Endpoints:**

- 62 1) Percent Time spent with glucose levels above 10.0 mmol/L
- 63 2) HbA1c
- 64 3) Mean of glucose levels
- 65 4) Percent Time spent with glucose levels below 3.9 mmol/L

66 **Secondary Efficacy Endpoints:**

67 CGM Metrics

68     Overall Glucose Control

69       1) Standard deviation of glucose levels  
70       2) Coefficient of variation of glucose levels

71     Hyperglycemia

72       3) Percent Time spent with glucose levels above 16.7 mmol/L

73     Hypoglycemia

74       4) Percent Time spent with glucose levels below 3.5 mmol/L  
75       5) Percent Time spent with glucose levels below 3.0 mmol/L  
76       6) Area under the curve of glucose levels below 3.5 mmol/L  
77       7) Area under the curve of glucose levels below 3.0 mmol/L

78     Insulin Delivery

79       8) Total insulin dose  
80       9) Basal insulin dose  
81       10) Bolus insulin dose

82     Clinical Metrics

83       11) BMI standard deviation score

84     Questionnaires

85       12) Strengths and Difficulties Questionnaire  
86            ○ Emotional Problems Subscale  
87            ○ Conduct Problems Subscale  
88            ○ Hyperactivity Subscale  
89            ○ Peer Problems Subscale  
90            ○ Prosocial Subscale  
91            ○ Total Difficulties Score

92       13) Hypoglycemia Fear Survey  
93            ○ Behavior Subscale  
94            ○ Worry Subscale

95       14) WHO-5

96       15) Epworth Sleepiness Scale

97       16) Pittsburgh Sleep Quality Index  
98            ○ Subjective Sleep Quality Subscale  
99            ○ Sleep Latency Subscale  
100           ○ Sleep Duration Subscale  
101           ○ Habitual Sleep Efficiency Subscale  
102           ○ Sleep Disturbances Subscale  
103           ○ Use of Sleeping Medication Subscale  
104           ○ Daytime Dysfunction Subscale

105       17) Children's Sleep Habit Questionnaire  
106           ○ Bedtime Resistance Subscale  
107           ○ Sleep Onset Delay Subscale  
108           ○ Sleep Duration Subscale  
109           ○ Sleep Anxiety Subscale  
110           ○ Night Waking Subscale  
111           ○ Parasomnias Subscale  
112           ○ Sleep Disordered Breathing Subscale

113                   ○ Daytime Sleepiness Subscale

114   All metrics listed above will be outcomes in the main study. In the extension phase, the same  
115   outcomes will be analyzed, with the exceptions of the Pittsburgh Sleep Quality Index and the  
116   Children's Sleep Habit Questionnaire. The primary outcome in the extension phase will be time  
117   in range calculated over the full 18 months.

118   **4.1 Calculation of CGM Metrics**

119   For the primary outcome and all secondary CGM metrics, a single value will be calculated for  
120   each subject for each period by pooling all CGM readings between the treatment initiation visit  
121   and up to 112 days post-initiation visit or the end of treatment visit, whichever comes first. All  
122   glucose sensor readings will be weighted equally in the pooled percentages regardless of how  
123   they distribute across weeks. Data will not be truncated due to protocol deviations.

124   Baseline CGM metrics will be calculated by pooling all readings up to the last 14 available days  
125   of CGM readings prior to randomization.

126   In the extension phase, CGM metrics will be calculated by pooling all readings inclusively  
127   occurring from the day after the last visit of the main study up until the last visit of the extension  
128   phase.

129   Additionally, CGM metrics will be calculated every three months during the extension phase by  
130   inclusively pooling all CGM readings falling within each of the windows specified at each month  
131   in the table below:

Month	Window for Analysis
Month 3	Days 1-91
Month 6	Days 92-182
Month 9	Days 183-274
Month 12	Days 275-365
Month 15	Days 366-456
Month 18	Days 457-548

132

133   **4.2 Calculation of BMI SD Scores**

134   BMI standard deviation score will be calculated using the WHO growth chart.

135   **5. Analysis Datasets and Sensitivity Analyses**

136   **5.1 Analysis Cohorts**

- 137   • The primary analysis and all secondary analyses will be performed on a modified  
138   intention-to-treat basis with each day included in the treatment group assigned by  
139   randomization.
- 140   • A per-protocol analysis restricted to randomized participants with a minimum of 60% of  
141   available CGM readings during the control period and 60% CL system use during the CL  
142   period will be conducted for the primary outcome.
- 143   • Safety outcomes will be reported for all enrolled participants, regardless of whether the  
144   study was completed.

145 **6. Analysis of the Primary Efficacy Endpoint**

146 **6.1 Included Subjects**

147 In analyses conducted in the main study, only subjects with at least 168 hours of CGM data in at  
148 least one period will be included. If a subject has more than 168 hours of data in period 1 and  
149 then drops out of the study without any data in period 2, then he or she will be included in the  
150 analysis.

151 In the extension phase, analyses will include participants with at least 168 hours of CGM data  
152 during the SAP phase of the main study and at least 672 hours of CGM data during the extension  
153 phase. For the analyses conducted every three months during the extension phase, at least 168  
154 hours of CGM data will be required within a given three-month period to be included in the  
155 tabulations of summary statistics for that particular period.

156 **6.2 Missing Data**

157 Missing data will not be imputed for the primary analysis in this study.

158 **6.3 Statistical Methods**

159 Mean  $\pm$  SD or summary statistics appropriate to the distribution will be reported for the primary  
160 outcome and each of the key secondary outcomes listed below over the four month period by  
161 treatment intervention. Summary statistics also will be tabulated for the primary outcome during  
162 the extension phase. For the main study, the treatment interventions will be compared using a  
163 linear mixed model adjusting for period as a fixed effect and site as a random effect. The analysis  
164 dataset will be three records per subject (one for baseline and one for each period). Inclusion of  
165 the pre-randomization baseline value as a third observation for each subject in the model gives a  
166 variance reduction analogous to adjusting for it as a covariate. Baseline is not modeled as a  
167 covariate in this analysis because there is no corresponding baseline for period 2, only pre-  
168 randomization. Note that adjusting for a post-randomization period 2 baseline can introduce a  
169 bias so that is not done here. The model will account for correlated data from the same subject.  
170 A 95% confidence interval will be reported for the difference between the interventions based on  
171 the linear mixed model.

172 Residual values will be examined for an approximate normal distribution. If values are highly  
173 skewed, then a ranked normal score transformation will be used instead. However, previous  
174 experience suggests that the primary outcome will follow an approximately normal distribution.  
175 A separate model will also be built with the inclusion of a period by treatment interaction to  
176 assess for the presence of a carryover effect. We do not expect a carryover effect to be present. A  
177 two-sided p-value will be reported.

178 For the primary endpoint and other key endpoints listed in section 4, the familywise type I error  
179 rate (FWER) will be controlled at two-sided  $\alpha = 0.05$ . A gatekeeping strategy will be used, where  
180 the primary endpoint will be tested first, if passing the significance testing, other key endpoints  
181 will be tested in the order listed below using the fixed-sequence method at  $\alpha = 0.05$ :

- 182 • Time spent with sensor glucose levels between 3.9 to 10.0 mmol/l
- 183 • Time spent above target glucose (10.0 mmol/l)
- 184 • HbA1c

185     • Average of glucose levels  
 186     • Time spent below target glucose (3.9 mmol/l)

187 This process continues iteratively moving to the next variable down on the list until a non-  
 188 significant result ( $p \geq 0.05$ ) is observed, or all five variables have been tested. If a non-  
 189 significant result is encountered, then formal statistical hypothesis testing is terminated and any  
 190 variables below on the list are not formally tested and analysis of these variables becomes  
 191 exploratory.

192  
 193 For example, in the hypothetical scenario depicted in the table below, the first three outcome  
 194 variables both have a significant result so testing continues to the fourth variable (CGM mean  
 195 glucose). The result is not significant for that fourth variable ( $p = 0.33$ ) so testing stops. No  
 196 formal hypothesis test is conducted for the fifth variable on the list in this example scenario.

HIERARCHICAL ORDER	OUTCOME VARIABLE	TREATMENT ARM P-VALUE	SIGNIFICANT?	ACTION
1 st	CGM % 3.9-10.0 mmol/L (primary outcome)	0.001	Yes	Test next variable
2 nd	CGM % above 10.0 mmol/L	0.02	Yes	Test next variable
3 rd	HbA1c	0.007	Yes	Test next variable
4 th	CGM mean glucose	0.33	No	Stop formal testing
5 th	CGM % below 3.9 mmol/L	Not tested	Unknown	N/A

197  
 198 Regardless of the results of the hierarchical testing, summary statistics appropriate to the  
 199 distribution will be tabulated by treatment arm for each hierarchical outcome. A 95% confidence  
 200 interval for the treatment arm difference will also be calculated for all five hierarchical outcomes  
 201 listed above. However, a confidence interval that excludes zero will not be considered a  
 202 statistically significant result if an outcome variable higher on the hierarchical list failed to reach  
 203 statistical significance.

204  
 205 In the extension phase, the primary analysis will involve performing a paired t-test to compare  
 206 the mean time in range between the extension phase and the SAP period of the main study. If the  
 207 outcome is skewed, then a nonparametric test will be used instead.

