# **14 Data Analysis**

## **14.1 Primary Endpoint Analysis**

The primary analysis will evaluate the between group difference in time spent in the target glucose range from 3.9 to 10.0 mmol/l (70 to 180 mg/dl) based on CGM glucose levels during the four month intervention periods.

Mean  $\pm$  SD or summary statistics appropriate to the distribution will be reported for the primary endpoint over the four month period by treatment intervention. The treatment interventions will be compared using a linear mixed model adjusting for period as a fixed effect and site as a random effect. The model will account for correlated data from the same subject. A 95% confidence interval will be reported for the difference between the interventions based on the linear mixed model.

Residual values will be examined for an approximate normal distribution. If values are highly skewed, then a ranked normal score transformation will be used instead. However, previous experience suggests that the primary endpoint will follow an approximately normal distribution. A separate model will also be built with the inclusion

of a period by treatment interaction to assess for the presence of a carryover effect. A two-sided p-value will be reported.

The primary analysis will be a single statistical comparison of a single outcome measure. No formal corrections for multiple comparisons will be performed for the secondary analyses in this study.

The primary analysis will be performed on an intention-to-treat basis using the treatment order assigned by randomization. Only subjects with the minimum number of hours of CGM data as specified in the analysis plan will be included.

A per-protocol analysis restricted to participants with a minimum of 60% CGM data during control period and 60% use of closed-loop during closed-loop period will be conducted for the primary endpoint.

A detailed analysis plan will be provided separately.

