## **14.4 Extension Phase Analyses**

### **14.4.1 Primary Endpoint Analysis**

The primary analysis will evaluate the difference in time spent in the target glucose range, between 3.9 to 10.0 mmol/l (70 to 180 mg/dl) as recorded by CGM, over 18

months from the end of the primary phase, as compared to sensor augmented pump therapy during the primary study phase.

Mean  $\pm$  SD or summary statistics appropriate to the distribution will be reported for the primary endpoint for the sensor augmented pump phase of the main study and over the extension period. During the extension period, the primary outcome will be calculated by pooling all CGM readings occurring throughout the entire extension phase. This will include all readings from the day after the last visit of the main study up until the final day of the extension phase. A paired t-test will be used to compare values using sensor augmented pump to values during the extension phase. If the outcome is skewed, then a nonparametric test will be used instead.

However, previous experience suggests that the primary endpoint will follow an approximately normal distribution. Analyses will include individuals with at least 168 hours (1 week) of CGM data during the sensor augmented pump phase and at least 672 hours (4 weeks) of CGM data during the extension phase

A detailed analysis plan will be provided separately.

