## 208 7. Analysis of the Secondary Endpoints

### 209 7.1 Included Subjects

210 In the analyses involving HbA1c and BMI standard deviation score, all subjects with an  
 211 available measurement within the analysis windows specified in section 7.3 will be included.

212 For secondary CGM metrics, inclusion criteria will be the same as the primary analysis.

213 For the secondary insulin outcomes computed during the main study, at least 168 hours of insulin  
 214 data in at least one period will be required for inclusion. If a subject has more than 168 hours of

215 insulin data in period 1 and then drops out of the study without any data in period 2, then he or  
216 she will be included in the analysis.

217 For the secondary insulin outcomes calculated during the extension phase, analyses will include  
218 participants with at least 168 hours of insulin data during the SAP phase of the main study and at  
219 least 672 hours of insulin data during the extension phase.

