## 370 **9. Adherence and Retention Analyses**

### 371 **9.1 Utility Analysis**

372 The amount of CGM use will be tabulated for each treatment arm, in addition to the amount of  
373 closed loop system use in the CL arm. Summary statistics appropriate to the distribution and  
374 range will be reported for the percentage of time using the CGM over the four month period (as  
375 defined above) for each treatment group. The same will be done for the percentage of time using  
376 the closed loop system in the CL arm. Tabulations of summary statistics will also be performed  
377 for the percentage of time spent using the closed loop system while using the CGM in the CL  
378 arm.

379 The percentage of time spent using the CGM will be calculated by dividing the total number of  
380 CGM readings by the expected number of readings during the four-month period. The  
381 percentage of time using the closed loop system in the CL arm will be calculated by dividing the  
382 total amount of time that temporary basal infusion lasts no more than 30 minutes by the  
383 maximum possible amount of time that the system could have been used. The percentage of time  
384 using the closed loop system while using the CGM (in the CL arm) will then be computed by  
385 dividing the time that the closed loop system was operational by the amount of time that the  
386 CGM was available.

387 If a subject drops out of the study in the middle of a period, then the subject will be counted as  
388 not using the CGM or the closed loop system at all during the remainder of the study. Thus, these  
389 time points will be counted as zero use in the calculation of CGM use and closed loop system  
390 use.

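### Should the 168-hour CGM minimum in SAP 6.1 apply to each period value rather than to each child?

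*Combined protocol and SAP*

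**What the plan says.** Protocol 14.1 leaves the threshold to the analysis plan and words it by child: "Only subjects with the minimum number of hours of CGM data as specified in the analysis plan will be included".

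SAP 6.1 supplies the number: "In analyses conducted in the main study, only subjects with at least 168 hours of CGM data in at" least one period. Its only worked example is a child who passes 168 hours in period 1 and leaves with no period 2 data; that child stays in. A second period with some data but under 168 hours is not discussed.

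SAP 4.1 sets no lower limit: "For the primary outcome and all secondary CGM metrics, a single value will be calculated for" each child and period, from all readings up to day 112. In SAP 6.3 each child contributes a baseline record and one record per period, and no weighting by hours is stated. SAP 7.1 repeats the rule for insulin: 168 hours of "data in at least one period will be required for inclusion".

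The extension phase is stricter. Protocol 14.4.1 asks for "at least 168 hours (1 week) of CGM data during the sensor augmented pump phase" and 672 hours in the extension, and SAP 6.1 asks for 168 hours within each three-month window.

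**The concern.** Read literally, the rule is uneven. A child with 168 hours in one period and 1 hour in the other contributes two values, while a child with 167 hours in each contributes none. The 1-hour value is described as time in range over four months and enters the model like a value from 112 days. Because the plan sets minimums by phase and window in the extension, the main-study wording can look like an oversight.

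At stake would be the precision of the primary comparison and, if short values fell mainly in one arm, its direction. No planned table counts such values.

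**Working it through.** **1. The plan's own figure.** Inputs from protocol 14.12 and SAP 3: difference 5 points, SD 10.3, correlation 0.3, 90% power; two-sided 0.05 from SAP 6.3. The SD of the within-child difference is 10.3 × √(2 × (1 − 0.3)) = 12.19. With the noncentral t distribution, power is 0.898 at 64 children and 0.903 at 65, so 65 reproduces. Then 65 × 1.1 = 71.5, rounded up to 72.

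**2. Scale of the threshold.** 112 days is 2,688 hours. So 168 hours is 6.25% of a full period and 24 hours is 0.9%.

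**3. One short value.** Take 72 children in two sequences of 36, with period and treatment fixed. The variance of the treatment difference is 12.19²/72 = 2.063, the SE is 1.436, and power is Φ(5/1.436 − 1.96) = 0.936. Each period value has weight 1/(2 × 36) = 1/72, so a short value with extra SD s adds s²/5184 to the variance. Here s = daily SD/√(hours/24). The documents give no daily SD; I assume 10, 15 or 20 points and independent days. For example, 6 hours at daily SD 20 gives s = 40 and √(2.063 + 1600/5184) = 1.540. If the short value is set to missing and the other period kept, generalised least squares gives an SE of 1.443.

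| Hours in the short period | Extra SD s (daily SD 10/15/20) | SE if kept | Change against 1.443 |
|---|---|---|---|
| 6 | 20/30/40 | 1.463/1.495/1.540 | +1.4/+3.6/+6.7% |
| 24 | 10/15/20 | 1.443/1.451/1.463 | 0.0/+0.6/+1.4% |
| 48 | 7.1/10.6/14.1 | 1.440/1.444/1.450 | −0.2/+0.1/+0.5% |
| 96 | 5.0/7.5/10.0 | 1.438/1.440/1.443 | −0.3/−0.2/0.0% |
| 144 | 4.1/6.1/8.2 | 1.437/1.439/1.441 | −0.4/−0.3/−0.1% |

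Keeping and dropping break even at s of about 9.9, that is at about 1, 2.3 and 4 days for daily SD 10, 15 and 20. A 168-hour floor would therefore discard values that help.

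**4. Several short values.** With 65 children (33 and 32 per sequence), the variance without short values is (12.19²/4) × (1/33 + 1/32) = 2.286. Each short value in the larger sequence adds s²/(4 × 33²) = s²/4356. Power by the same normal formula, for daily SD 10/15/20:

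| Short values | 72 children | 65 children |
|---|---|---|
| None | 0.94 | 0.91 |
| One of 6 h, or four of 24 h | 0.93/0.92/0.90 | 0.90/0.89/0.87 |
| Two of 6 h | 0.92/0.90/0.86 | 0.89/0.86/0.82 |
| Four of 6 h | 0.90/0.85/0.79 | 0.87/0.81/0.73 |

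The two cases in the second row coincide because four values at s add the same variance as one at 2s.

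**5. Shift in the estimate.** If a short value is 15 points off (assumed), the estimate moves by 15/72 = 0.21 points. Four such values move it by 0.83 points if all fall in one arm and err the same way, and by about zero if split evenly.

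**6. The excluded child.** A child with 167 hours in both periods gives an SE of 1.438/1.441/1.444 if kept and 1.446 if excluded. The difference is at most 0.008, or 0.6%.

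**The case for a change.** The best case for acting is about reporting. SAP 9.1 gives the range of CGM use by arm, but a child who leaves mid-period is counted as "not using the CGM or the closed loop system at all during the remainder of the study". One period 1 drop-out therefore puts the minimum in the other arm at 0%, and the range no longer shows whether a short value entered the model. The flow charts in SAP 9.2 count children and visits, not period values. SAP 5.1 has "A per-protocol analysis restricted to randomized participants with a minimum of 60% of" available CGM readings in the control period, which removes short values there, but it also requires 60% closed-loop use in the other period. A change in that result could not be put down to short values alone. Short values might also be unbalanced, since protocol 9.8.1 has a competency check only at closed-loop start. A count by arm and period would cost almost nothing.

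The reporting gap stands: nothing planned gives the count. The rest is weaker.

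- Very short periods are not shown to occur. Protocol 9.6 requires 8 days of CGM data in the last 14 of run-in, protocol 9.9 schedules contacts at 24 to 48 hours, one week and monthly, and protocol 9.15 aims to keep children in follow-up after stopping the intervention.
- The planned outputs show part of the picture. Early period 2 drop-outs appear in the flow charts. Without a period 1 drop-out, the SAP 9.1 minimum reveals any very short period. SAP 6.3 also examines residuals and provides a rank-based transformation for highly skewed values.
- The imbalance is conjecture. The documents do not say whether a family that fails the closed-loop check would produce any readings in that period.
- The stricter extension rule supports a paired test, which needs both values. It is not evidence that the main-study rule is wrong.

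The worst rows in step 4 need four of the roughly seven drop-outs allowed for (72 − 65) to leave within hours of starting a period.

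**Conclusion.** The reading of the text is right, and no change to the plan follows. Keeping all observed data is a fair trade-off under modified intention to treat. Against setting the value to missing, keeping one day of data costs at most 1.4% in standard error, and keeping four days or more costs nothing or helps slightly. With 72 complete children, power stays at about 0.90 or above for one 6-hour value or up to four one-day values. With the planned 65 it is about 0.90 to 0.87. Only several values of a few hours each would matter, and nothing in the documents points to that.

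A per-period floor would exclude on post-randomisation behaviour and rely on a missing-at-random assumption. Its cut-off would also be chosen late, because SAP version 3.0 is dated after the initial analyses were completed. The sponsor may state how many period values rest on fewer than 168 and fewer than 24 hours, by treatment and period. That can be reported without altering the plan.

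These sizes rest on an assumed day-to-day SD of 10 to 20 points, independence between days, and the plan's SD of 10.3 and correlation of 0.3.
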